11.2.2.7 Blood pressure increase

- Time to first exacerbation of hypertension During Weeks 28 to 52

Time to first exacerbation during weeks 28 to 52 will be analyzed and compared between the 2 treatment groups using the Cox Proportional Hazards model adjusting for treatment group and stratification factors.

Superiority of roxadustat vs. Epoetin will be declared if the upper bound of the 2-sided 95% confidence interval of the hazard ratio is less than 1.

Subjects will be censored at the time of the last available blood pressure if an exacerbation in blood pressure does not occur.

Sensitivity analysis will be performed on proportion of subjects with increase in blood pressure at any time during the study, defined as an increase from baseline of ≥ 20 mm Hg systolic BP and sBP >170 mmHg or an increase from baseline of ≥ 15 mm Hg diastolic BP and dBP >100 mmHg. Increases from baseline in blood pressure are considered as confirmed by taking the mean of triplicates. The proportion of subjects with increase in blood pressure will be compared between the 2 treatment groups using logistic regression model adjusting for baseline predialysis systolic and diastolic BP as covariates and treatment group and stratification factors as fixed effects.

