##### 3.2.2 Secondary Efficacy Endpoints

The secondary efficacy endpoints in this study are:

- US (FDA) submission: Proportion of subjects with mean Hb level during the evaluation period defined as Week 28 until Week 52  $\geq 10.0$  g/dL.
- EU regulatory submission: Hemoglobin (Hb) response, defined as mean Hb during Weeks 28 to 36 within the target range of 10.0 to 12.0 g/dL without having received rescue therapy within 6 weeks prior to and during this 8-week evaluation period.
- Average monthly IV iron use per subject during Weeks 1 to 36 (monthly defined as a period of 4 weeks).
- Change from BL in low-density lipoprotein (LDL) cholesterol to the average LDL cholesterol of Weeks 12 to 28
- Change from BL in SF-36 Physical Functioning (PF) subscore to the average PF subscore of Weeks 12 to 28
- Change from BL in SF-36 Vitality (VT) subscore to the average VT subscore of Weeks 12 to 28
- Effect on predialysis BP:
  - Time to an exacerbation of hypertension from BL during Weeks 1 to 36

- An increase from BL of  $\geq 20$  mm Hg systolic blood pressure (sBP) and sBP  $> 170$  mmHg

OR

- An increase from BL of  $\geq 15$  mm Hg diastolic blood pressure (dBP) and dBP  $> 100$  mmHg
- Change from BL in mean arterial pressure (MAP) to the MAP value averaged over Weeks 20 to 28

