4.2 Secondary Efficacy Endpoints

The secondary efficacy endpoints in this study are as below for both US and Ex-US submission unless otherwise specified:

- US (FDA) submission: Proportion of subjects with mean hemoglobin level during the evaluation period defined as Week 28 until Week 52 ≥ 10.0 g/dL.
- Ex-US submission: Proportion of subjects with hemoglobin response, defined as mean hemoglobin during Weeks 28 to 36 within the target range of 10.0 to 12.0 g/dL without having received rescue therapy within 6 weeks prior to and during this 8-week evaluation period.
- Change from baseline in Low Density Lipoprotein (LDL) cholesterol to the average LDL cholesterol of weeks 12 to 28.
- Hemoglobin change from baseline to the average level during the Weeks 18 to 24 for subjects with baseline hs-CRP $>$ ULN.
- Average monthly IV iron use per subject during the Treatment Period during Weeks 28 to 52 (monthly defined as a period of 4 weeks).
- Time to first RBC Transfusion during the treatment
- Change from BL in mean arterial pressure (MAP) to the MAP value averaged over weeks 20 to 28
- Time to first exacerbation of hypertension: An increase from BL of ≥ 20 mm systolic blood pressure (SBP) and SBP ≥ 170 mmHg or an increase from baseline of ≥ 15 mmHg diastolic blood pressure (DBP) and DBP ≥ 100 mmHg during Weeks 28 to 52.

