 - Hospitalization-free survival days on treatment up to Week 52, 7 days after Last Dose. The days will be compared between the 2 treatment groups using ANCOVA model with baseline Hb and the baseline stratification factors.
 - Number of days on treatment out of hospital and skilled nursing facility up to Week 52, 7 days after Last Dose. Similar analysis as above will be performed.

- **Missed Dialysis:**
 - Occurrence (number) of missed dialysis sessions per subject.
 - Proportion of subjects with missed dialysis sessions.
 - Number of days of missed dialysis sessions per patient-exposure year (PEY).
- **Rescue Therapy Use:**
 - Proportion of subjects who receive RBC/blood transfusions.
 - Number of RBC/blood packs per subject-month exposure to study medication.
 - Proportion of subjects who received rescue therapy [composite of RBC transfusions and/or rescue ESA].
 - Time to initial rescue therapy.
- **Changes in Cholesterol Levels:**
 - Change from baseline at each of the selected treatment time points (Weeks 12-28, every 8 weeks onward until Week 52) in:
 - total cholesterol,
 - low-density lipoprotein/high-density lipoprotein ratio,
 - Non-HDL cholesterol.
 - Proportion of subjects achieving LDL target of <100 mg/dL averaged over Weeks 12-28 of treatment for subjects whose baseline LDL \geq 100.
- **Blood Pressure Effect:**
 - Proportion of subjects achieving blood pressure treatment goal in ESRD subjects (predialysis systolic BP <140 mmHg and diastolic BP <90 mmHg) averaged over Weeks 12-28.
 - Time to first exacerbation of hypertension from baseline during weeks 1 to 36 defined as:
 - An increase from baseline of \geq 20 mmHg systolic BP (SBP) and SBP >170 mmHg
 - Or,
 - An increase from baseline of \geq 15 mmHg diastolic BP (DBP) and DBP >100 mmHg
 - Time to a treatment-emergent AE of hypertension.
 - Time to exacerbation from baseline of antihypertensive therapy.
 - Proportion of subjects with exacerbation of hypertension, defined as an increase from baseline of \geq 20 mmHg systolic BP and sBP >170 mmHg or an increase from baseline of \geq 15 mmHg diastolic BP and dBP >100 mmHg.
 - Proportion of subjects with a treatment-emergent AE of hypertension.
 - Proportion of subjects with exacerbation from baseline of antihypertensive therapy.
- **Vascular Access Thrombosis (HD subjects):**
 - Time to a treatment-emergent AE of vascular access thrombosis
 - Proportion subjects with a treatment-emergent AE of vascular access thrombosis

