11.2 Analysis of Secondary Endpoints

11.2.1 Secondary Endpoints and Hypothesis Testing

Once the null hypothesis of the primary endpoint has been rejected, the secondary endpoints below will be tested using a fixed sequence testing procedure, in order to maintain the overall two-sided type I error of 0.05. If the claim of superiority or non-inferiority is successful and the test will progress to the next comparison in sequence as follows.

Table 6 Key Secondary Endpoints Fixed Sequence Testing Procedure

Test	Variable	Comparison
1	Proportion of subjects with mean hemoglobin level during the evaluation period defined as Week 28 until Week 52 \geq 10.0 g/dL (U.S.) or Proportion of Hb responders in the average of weeks 28 to 36 within the target range of 10.0 to 12.0 g/dL without having received rescue therapy. (Ex-U.S.).	Non-inferiority of roxadustat versus EPO with margin of -0.15
2	LDL cholesterol change from BL to the average of weeks 12 to 28.	Superiority of roxadustat versus EPO
3	Hemoglobin change from baseline to the average level during Weeks 18 to 24 for subjects with baseline hsCRP > ULN	Non-inferiority of roxadustat versus EPO
4	Average monthly IV iron (mg) use per subject during weeks 28 to 52.	Superiority of roxadustat versus EPO
5	Time to first RBC Transfusion during the treatment.	Non-inferiority of roxadustat versus Epo with margin of 1.8
6	MAP change from BL to the average MAP of weeks 20 to 28.	Superiority of roxadustat versus EPO
7	Time to first exacerbation of hypertension: An increase from baseline of \geq 20 mmHg systolic blood pressure (SBP) and SBP \geq 170 mmHg or an increase from baseline of \geq 15 mmHg diastolic blood pressure (DBP) and DBP \geq 100 mmHg during Weeks 28 to 52.	Superiority and Non-inferiority of roxadustat versus EPO with margin of 1.8

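### Key secondary Test 7 counts hypertension exacerbations only in Weeks 28 to 52, with no reason given, where the protocol counts them from baseline over Weeks 1 to 36

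*SAP*

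**What the plan says.** **Protocol.** Section 3.2.2 lists the secondary endpoint as "Time to an exacerbation of hypertension from BL during Weeks 1 to 36". Section 9.4.3.2 places it in the fixed sequence, with a Cox model and a superiority criterion. Section 9.6 commits the sponsor to highlighting significant changes to the planned analyses in the SAP.

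**SAP, confirmatory test.** Section 4.2 ends the endpoint definition with "mmHg during Weeks 28 to 52". Table 6 (section 11.2.1) repeats that window for Test 7, and section 11.2.2.7 says "Time to first exacerbation during weeks 28 to 52 will be analyzed and compared between the 2 treatment groups". Table 6 belongs to a sequence set up "in order to maintain the overall two-sided type I error of 0.05".

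**SAP, protocol window.** It survives in section 4.3 as an additional evaluation: "Time to first exacerbation of hypertension from baseline during weeks 1 to 36 defined as". Under section 5.3, tests outside the sequence get no multiplicity adjustment.

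**SAP, rules for Test 7.** Section 11.2.2.7 says "Subjects will be censored at the time of the last available blood pressure if an exacerbation in blood pressure does not occur". It does not say whether time starts at Day 1 or Week 28, whether a subject with an exacerbation before Week 28 is removed or may count again, or how subjects who stop before Week 28 are handled. The opening of section 11 sets a default period for efficacy time-to-event analyses that begins at first dose. Test 7 departs from that default.

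**Two further mismatches in the same test.** Table 6 gives the comparison as "Superiority and Non-inferiority of roxadustat versus EPO with margin of 1.8", while section 11.2.2.7 has only a superiority criterion, with a limit of 1: "Superiority of roxadustat vs. Epoetin will be declared if the upper bound of the 2-sided 95% confidence interval of the hazard ratio is less than". SAP 4.2 and Table 6 use thresholds of at least 170 mmHg systolic or at least 100 mmHg diastolic. Protocol 3.2.2, SAP 4.3 and the sensitivity analysis in 11.2.2.7 use strictly above those values.

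**The concern.** Randomization protects a time-to-first-event comparison when follow-up starts at or near randomization. A window that opens 28 weeks later compares only subjects still observed then. Stopping before Week 28 happens after randomization, and in an open-label trial it can differ by arm. Minimum treatment may also be shortened for subjects enrolled under Amendments 1 and 2 (Protocol 4.1), so some of them may not complete the window.

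The omitted weeks matter for this endpoint. They contain the switch from the prior ESA, and roxadustat dose adjustment starts at Week 4 (Protocol 4.5.3.1). Protocol 2.2 names hypertension as an ESA risk, and Protocol 2.3 lists absence of a hypertensive effect among roxadustat's potential advantages. A superiority claim on this topic that omits the first 28 weeks answers a narrower question than the protocol's endpoint, and with fewer events.

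**Working it through.** **1. The plan's own figures.** No event rate, event count or power is given for Test 7. The only power figure (at least 99% with 600 subjects, SAP 5.1) concerns the primary hemoglobin test. It reproduces: the distance to the margin is 0.75 - 0.30 = 0.45, the SE is 1.25 x sqrt(2/300) = 0.102, and 0.45/0.102 - 1.96 = 2.45, which gives 99.3%. It says nothing about Test 7.

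**2. Visits (SAP section 3).** Weeks 1 and 2, then every 2 weeks from Week 4 to Week 24: 2 + 11 = 13 visits before the window. Weeks 28, 32, ..., 52: 7 visits in it. 13/20 = 65% of scheduled post-baseline visits to Week 52 precede the window. Vital signs are taken at all of them.

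**3. Share of first-year first events before Week 28.** The 52-week incidence c is assumed.
- Constant weekly hazard: [1 - (1-c)^(28/52)] / c. For c = 0.20, (1 - 0.887)/0.20 = 0.566. For c from 5% to 50%, the range is 55-62%.
- Constant probability per visit, with q = (1-c)^(1/20): (1 - q^13)/(1 - q^20). For the same c, 66-73%.
- Simulation, control arm, c from 20% to 40%, gamma frailty variance 0.5-2, 20% dropout by Week 28: 63-76%.

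The share falls below half only if the weekly hazard after Week 28 is about 1.2-1.5 times the earlier one, or the per-visit probability about 2.0-2.4 times (c from 10% to 40%, no dropout).

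**4. What Test 7 shows if the true hazard ratio is 1.5 in Weeks 0-28 and 1.0 afterwards** (simulated event-rate ratios, same assumptions as the third line of step 3 except for the frailty shown):

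| Rule for subjects with an early exacerbation | Frailty variance | Weeks 28-52 |
|---|---|---|
| Excluded | none | about 1.0 |
| Excluded | 0.5-2 | 0.83-0.97 |
| May count again | 0-2 | about 1.0 |

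With frailty variance 0.5-2, the Weeks 1-36 ratio is 1.29-1.39.

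**5. Precision under constant hazard, no depletion or dropout.** Events are proportional to window length, so the ratio of standard errors of the log hazard ratio is the square root of the ratio of lengths.
- Against the protocol window: sqrt(36/24) = 1.22.
- Against Day 1 to Week 52: sqrt(52/24) = 1.47.

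**6. Events and power.** Assumed: 600 subjects, c from 20% to 40%, per-visit model, no dropout, hazard ratio 0.75. Power = Phi(|ln 0.75| x sqrt(d)/2 - 1.96), where d is the number of events. For d = 39: 0.288 x 6.24/2 - 1.96 = -1.06, which gives 14%.

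| Window | First events | Power |
|---|---|---|
| Weeks 28-52 | 39-70 | 14-23% |
| Weeks 1-36 | 98-201 | 30-53% |
| Weeks 1-52 | 120-240 | 35-61% |

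**The case against.** The case for leaving the plan alone has four parts.

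- **The window is deliberate.** It is the same in three SAP sections and matches the US primary evaluation period and Test 4 (IV iron). The primary endpoint also omits titration. This stands as evidence of intent. It does not answer the selection problem: the US primary analysis uses all randomized subjects and imputes missing values, whereas a Cox analysis opening at Week 28 gets nothing from subjects who have already left.
- **Early effects are looked at elsewhere.** The any-time proportion in 11.2.2.7, the Weeks 1-36 endpoint in 4.3, hypertension adverse events in 11.3.5 and vital signs in 12.3 all cover the early weeks. Test 6 covers mean arterial pressure over Weeks 20-28. This stands. A reader might infer that the trial cannot see an early pressor effect, and the documents do not support that. Early exacerbations are missing only from the alpha-controlled exacerbation test.
- **The size rests on assumptions.** A reader might infer that the window is known to discard most first events. That is likely under flat or falling hazards, but the documents give no rate and do not establish it.
- **Test 7 is last in the sequence.** No other claim depends on it. This limits the damage but does not make the claim sound.

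A reader might also infer that early harm would appear as benefit. That requires both frailty and the exclusion of early exacerbators, and the SAP states no such exclusion. If subjects with earlier events may count again, the ratio stays near 1.0. The supportable statement is that Test 7 misses an early difference.

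**Conclusion.** The concern holds as an unexplained change of window that weakens the confirmatory test. The text establishes that the SAP replaces Weeks 1-36 from baseline with Weeks 28-52, that no reason was found, and that exacerbations before Week 28 and subjects who stop before then do not inform the test. Whether the risk set at Week 28 is subjects without an exacerbation or everyone still observed cannot be settled, because the rule is missing. That gap is itself a reason to revise.

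The numbers are illustrations under assumed incidence, dropout and frailty: 55-76% of first-year first events before the window, and an early-only hazard ratio of 1.5 shrinking to about 1.0. The precision loss against the protocol's own window is about 1.22-fold under constant hazard. The figure of 1.47 applies only to a Day 1 to Week 52 analysis and should not be read as the cost of leaving the protocol. The change should be made, but nothing else in the testing sequence depends on it.

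**What to change.** In SAP 4.2, Table 6 and 11.2.2.7, define Test 7 as time from first dose to first exacerbation, over Weeks 1-36 (the protocol window) or Day 1 to Week 52. Use the Cox model and censoring rule already in 11.2.2.7, with censoring no later than the end of the window. Keep Weeks 28-52 as a supportive analysis, and state its time origin, its treatment of earlier exacerbations and its handling of subjects who stop before Week 28. If the sponsor prefers to keep Weeks 28-52 as the test, the SAP should give the reason and define the same three rules.

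In the same edit:
- use one set of thresholds (above, or at least, 170/100 mmHg) in SAP 4.2, 4.3, Table 6 and 11.2.2.7, and note any departure from the protocol;
- make Table 6 and 11.2.2.7 agree on whether non-inferiority with margin 1.8 is tested as well as superiority, and in what order.

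The cost is SAP wording and programming on data already collected. The Weeks 1-36 endpoint is listed in 4.3, but 11.3.5 supplies only a definition, so the model and censoring must be written in for it. The downside is that the Test 7 window would no longer match the US primary evaluation period.

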11.2.3 Secondary Analyses

The proportion of subjects who achieve a hemoglobin response may also be analyzed using logistic regression test and including baseline hemoglobin and stratification factors except mean qualifying screening hemoglobin (≤ 10.5 vs. >10.5 g/dL). The odds ratio (ROXADUSTAT vs. EPO) and its 95% confidence interval will be provided. . The non-inferiority margin is fixed as a difference of -0.15.

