5 GENERAL STATISTICAL CONSIDERATIONS

5.1 Sample Size Determination

At least 600 subjects and up to 1200 subjects will be randomized via IXRS to receive roxadustat or epoetin alfa in a 1:1 ratio. Study drug will be administered in an open-label manner. Randomization will be stratified by the following four factors:

- Mean qualifying screening hemoglobin (≤ 10.5 vs. >10.5 g/dL)
- History of cardiovascular, cerebrovascular or thromboembolic diseases (Yes vs. No)
- Mean prescribed baseline epoetin alfa dose (or, equivalent epoetin dose for non-epoetin subjects) in 4 weeks prior to randomization (≤ 150 vs. >150 IU/kg/week)

Up to 600 subjects will be enrolled in this study in each treatment group. During the course of this study, which is being conducted in parallel with other Phase 3 studies, up to 1200 subjects may be enrolled for safety evaluation of roxadustat in comparison to epoetin alfa including pre-specified and adjudicated safety events of interest (i.e., all-cause death, MI, stroke, congestive heart failure requiring hospitalization, unstable angina requiring hospitalization, DVT, pulmonary embolism, vascular access thrombosis, and hypertensive emergency). The final number of patients to be enrolled will be based on the enrollment rate of other studies within the same indication, in order to optimize stopping these studies at comparable time frame.

With at least 600 subjects, the study will provide at least 99% power to demonstrate statistical non-inferiority of roxadustat versus ESA in the primary endpoint for US (FDA) submission (i.e., specifically, hemoglobin change from baseline to the average level during the evaluation period defined as Week 28 until Week 52).

The study will provide at least 99% power to demonstrate statistical non-inferiority of roxadustat versus ESA in the primary endpoint outside of the United States (i.e., specifically, hemoglobin change from baseline in the averaged hemoglobin over Weeks 28 to 36). This assumes a difference (roxadustat minus ESA) of -0.30 g/dL, a non-inferiority margin for this difference of 0.75 g/dL and a standard deviation of 1.25 g/dL. Appendix 7 has description on the justification that the non-inferiority margin of 0.75 was used.

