5.3 Methodology and Conventions

Continuous variables will be presented by descriptive statistics: n, mean, standard deviation, median, minimum, and maximum. Categorical variables will be tabulated by frequency count and percentage. For efficacy endpoints, the standard error and 95% confidence intervals (CI) will be presented as part of the descriptive summaries.

Safety and efficacy data will be summarized and presented by treatment group and time point in summary tables.

Lab results obtained from the central laboratory will be used for all efficacy and safety analyses. Local laboratory values, if collected in the CRF's, will be listed only in data listing. Unless otherwise stated, all statistical tests will be two-sided hypothesis tests performed at the 5% level of significance for main effects and all confidence intervals will be two-sided 95% confidence intervals.

The secondary endpoints will be tested sequentially using the fixed sequence approach for multiplicity adjustments at an alpha level of 0.05. There will be no adjustments for multiple comparisons for other tests.

All analyses will be performed using SAS® Version 9.1.3 or higher.

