11.2.2.1 Proportion of Hemoglobin Responders

- US: Proportion of subjects with mean hemoglobin level during the evaluation period defined as Week 28 until Week 52 ≥ 10.0 g/dL, and patients with mean hemoglobin level between Hb 10-12 g/dL.
- Ex-US: Proportion of subjects with mean Hb between range of 10.0 to 12.0 g/dL without having received rescue therapy within 6 weeks prior to and during this 8-week evaluation period.

The hypothesis to be tested for the efficacy analysis is:

H0: Hemoglobin response rate for subjects in the roxadustat group - hemoglobin responder rate for subjects in the Epoetin group $\leq -15\%$

Versus

H1: Hemoglobin response rate for subjects in the roxadustat group - hemoglobin responder rate for subjects in the Epoetin group $> -15\%$.

A 2-sided 95% confidence interval for the difference of 2 responder rates (roxadustat – ESA) based on the Miettinen & Nurminen approach adjusting for treatment group and stratification factors will be calculated and non-inferiority will be declared if the lower bound of the 95% CI is greater than -15%.

Subjects who dropped out from the study before week 28 will be treated as non-responder.

11.2.2.2 Change from Baseline in LDL Cholesterol Averaged over Weeks 12 to 28

The change from baseline in LDL cholesterol will be analyzed and compared between the 2 treatment groups using MMRM model with baseline LDL cholesterol as a covariate and treatment group, visit, the interaction of treatment and visit, and the above mentioned stratification factors as fixed effects. The same strategy as that used in MMRM for Hb will be used to choose variance covariance structure. Data up to visit of Week 52 will be included in the model. The estimates for difference of LDL Cholesterol averaged over Weeks 12 to 28 between the two treatments groups will be generated from an estimate statement from Visit Week 12 to 28. Superiority will be declared if the upper bound of the 2-sided 95% confidence interval of the difference between roxadustat and active control does not exceed 0.

Baseline, LDL, is defined as the last available value obtained prior to the first dose of study drug.

11.2.2.3 Hemoglobin change from baseline to the average level during the Week 18 to 24 for Subjects with CRP > ULN

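### SAP 11.2.3 reports an odds ratio but sets its non-inferiority margin as a difference in proportions, so the criterion cannot be applied as written

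*SAP*

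**What the plan says.** The supportive analysis is in SAP 11.2.3 (Secondary Analyses) and is optional: "The proportion of subjects who achieve a hemoglobin response may also be analyzed using logistic regression test". The model includes baseline hemoglobin and the stratification factors other than screening hemoglobin. The only estimate promised is an odds ratio: "The odds ratio (ROXADUSTAT vs. EPO) and its 95% confidence interval will be provided". The next sentence sets the margin: "The non-inferiority margin is fixed as a difference of -0.15". The section ends there. It has no decision rule, no margin for the odds ratio, and no step from the fitted model to a difference in response rates.

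The main responder analysis, in SAP 11.2.2.1, is complete. Its interval is "A 2-sided 95% confidence interval for the difference of 2 responder rates (roxadustat – ESA) based on the Miettinen & Nurminen approach", and its rule is "non-inferiority will be declared if the lower bound of the 95% CI is greater than -15" percent. SAP 11.2.1, Table 6, lists this comparison as Test 1: "Non-inferiority of roxadustat versus EPO with margin of -0.15". Protocol 9.4.3.2 gives the same method and margin for the responder endpoint and does not mention a logistic model for it.

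**The concern.** A non-inferiority margin has a use only if the reported estimate can be held against it. An odds ratio is a positive number whose null value is 1; a margin of -0.15 belongs to a difference whose null value is 0. Elsewhere the SAP keeps the two together. In 11.2.2.1 a rate difference is set against -15%, and in 11.2.2.5 a hazard ratio is set against 1.8. The responder analysis in 11.2.3 is the place where a ratio estimate is paired with a difference margin.

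The stake is the usefulness of a robustness check. The logistic model adjusts for baseline hemoglobin, which 11.2.2.1 does not list, so it could add something to Test 1. As written, it gives the size and precision of an odds ratio but no defined threshold. The trial is open-label, and Protocol 9.6 asks for early SAP finalization to guard against bias. Leaving the scale open means it could be settled after results are known.

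**Working it through.** **Inputs.** Margin -0.15 (SAP 11.2.3 and Table 6). Two-sided 5% level (SAP 5.3: "all statistical tests will be two-sided hypothesis tests performed at the 5% level of significance"). Sample size (SAP 5.1: "At least 600 subjects and up to 1200 subjects will be randomized via IXRS to receive roxadustat or epoetin alfa in a 1:1 ratio"), hence 300 to 600 per arm. The epoetin responder rate p is not in the documents; it is assumed here at 50% to 90%.

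**The plan's own figure.** There is no stated power or rate for the responder endpoint. The only power figure is for the primary hemoglobin endpoint: at least 99% with 600 subjects, a true difference of -0.30, a margin of 0.75 and an SD of 1.25 g/dL. It reproduces: SE = 1.25 × √(2/300) = 0.102; (0.75 − 0.30)/0.102 − 1.96 = 2.45; power = 99.3%. This confirms the sample-size inputs but does not bear on 11.2.3.

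**Odds ratio equivalent to a 15-point deficit.** OR(p) = [(p − 0.15)/(1.15 − p)] / [p/(1 − p)].

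| Assumed epoetin rate | Roxadustat rate at the margin | Equivalent odds ratio |
|---|---|---|
| 50% | 35% | 0.538 |
| 60% | 45% | 0.545 |
| 70% | 55% | 0.524 |
| 80% | 65% | 0.464 |
| 85% | 70% | 0.412 |
| 90% | 75% | 0.333 |

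The value is nearly flat from 50% to 70% and then falls. These are unadjusted odds ratios. The conditional odds ratio from a model with baseline hemoglobin and strata will generally differ, so the table shows the order of size and does not supply margins for that model.

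**Three readings of the margin sentence.** Pass rates at a true deficit of exactly 15 points come from 200,000 simulated trials per setting, with unadjusted Wald 95% intervals.

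1. *Lower limit of the odds ratio above -0.15.* This always holds, because an odds ratio is positive. For example, 20% against 90% responders with 300 per arm gives OR = 0.25/9 = 0.028. The SE of the log odds ratio is √(1/60 + 1/240 + 1/270 + 1/30) = 0.241, so the lower limit is 0.017, still above -0.15.
2. *Lower limit of the log odds ratio above -0.15.* This means an odds ratio above e^(−0.15) = 0.861, equivalent to a deficit of only 3.7 points at p = 50% and 1.4 points at p = 90%. At a true 15-point deficit, 0% pass. With equal true rates, SE = √(2/[n p(1 − p)]). For p = 80% and n = 300 this is 0.204, and 0.15/0.204 − 1.96 = −1.225, a pass rate of 11%. Across p = 70% to 90% it is 13% down to 8% with 300 per arm, and 22% down to 12% with 600.
3. *Lower limit of the risk difference above -0.15.* At a true 15-point deficit, 2.4% to 2.7% pass, which is the nominal 2.5%. With equal true rates and n = 300, p = 80%: SE = √(2 × 0.16/300) = 0.0327, and 0.15/0.0327 − 1.96 = 2.63, a pass rate of 99.6%.

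Only the third reading behaves as a non-inferiority test with a 15-point margin.

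**The case against.** A reader might infer that the criterion can never fail, and that the analysis would then be reported as confirming non-inferiority. The documents do not support either step. SAP 11.2.3 never says that the odds-ratio limit is compared with -0.15. It calls the margin a difference, which points to the difference in proportions used in 11.2.2.1 and Table 6, and on that scale the test can fail. Nor does it contain a declaration rule, although the SAP writes one where it wants one, as in 11.2.2.1, 11.2.2.5 and 11.2.2.6. Guaranteed success belongs only to the least plausible of the three readings.

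The strongest case for leaving the text alone has three further parts. First, nothing confirmatory depends on it: the analysis is optional and Test 1 uses the Miettinen & Nurminen interval. That stands, and it limits the importance of the point. Second, an odds ratio with its interval still shows direction, size and precision. That also stands; what is missing is a usable threshold. Third, the SAP reference list includes a paper on covariate-adjusted differences in proportions from logistic regression, so the risk-difference scale may be what was meant. That is plausible, but 11.2.3 does not cite the paper or describe the step, and a programmer following the text would produce only the odds ratio.

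**Conclusion.** The mismatch is real and the finding is minor. SAP 11.2.3 gives a margin that cannot be applied to the only estimate it specifies. Depending on the scale chosen, the same sentence yields an empty test, a test that roxadustat would usually fail even with identical response rates (8% to 13% pass with 300 per arm), or a valid test at about 2.5%. No single odds-ratio margin follows from -0.15, because the equivalent runs from about 0.54 at an epoetin rate of 50% to 0.33 at 90%.

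These sizes rest on assumed responder rates and unadjusted calculations. The mismatch itself does not: an adjusted odds ratio is also positive and also not a difference. Test 1, the type I error of the fixed sequence and the later tests are unaffected.

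**What to change.** In SAP 11.2.3, state that predicted response probabilities from the logistic model will be averaged over the analysis population under each treatment. Their difference, roxadustat minus epoetin, is the covariate-adjusted risk difference. Specify how its 95% confidence interval is obtained, compare the lower bound with -0.15, and report the odds ratio and its interval descriptively. The reference-list paper on covariate-adjusted differences can be cited there if its method is the one adopted.

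If the sponsor wants only the odds ratio, delete the margin sentence.

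The cost is a few lines of SAP text and code. No new data are needed, and the sample size and testing sequence do not change.
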